7. The RHC will contact the patient to arrange the first RHC visit (sections 5.1 & 11.1.2), which must be within 28 days of registration, and at which eligibility for the trial must be reconfirmed

8. For patients still eligible for the trial, the RHC will fax a fully completed eligibility confirmation form to Leeds CTRU (see point 12 below). If there are any queries about eligibility, trial staff at Leeds CTRU will contact staff at the RHC immediately
9. Leeds CTRU will confirm the patient's inclusion in the trial and also confirm their registered dose level by fax to the main contact at site and the site pharmacy
10. During the dose escalation phase, the treatment start date must be confirmed and agreed with Leeds CTRU. A minimum of 15 days must have elapsed between the start of treatment of the first patient in each cohort and subsequent patients
11. For patients found to be ineligible for the trial, the RHC will fax a fully completed withdrawal form to Leeds CTRU
12. If there is a ≥ 21 day delay in starting trial treatment after completion of eligibility confirmation form at the RHC, a second eligibility confirmation form must be completed. Patients must start treatment within 6 weeks of completion of the initial eligibility confirmation form at the RHC
13. If after registration a patient decides to withdraw consent to the trial, or is found not to satisfy the eligibility criteria, the site must inform CTRU. Sites must complete a withdrawal form to confirm withdrawal details

Please see protocol section 11 for assessment summary and Appendices 6 and 7 for diagnostic sample requirements and investigations.

Once a patient has been registered onto the trial they must be provided with the following:

- A copy of their signed consent form and patient information sheet
- A patient contact card. Site on-call contact details for 24 hour medical care must be added to this card and patients advised to carry this with them at all times while participating in the trial
- A patient Red Flag card. A list of symptoms which need urgent medical attention

8. Trial Treatment

For the purpose of this protocol, the IMPs are **Carfilzomib, Thalidomide and Dexamethasone**.

All trial patients must be treated according to the following schedule in order to isolate the effects of the Carfilzomib.

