11.0 Assessments

The trial consists of an initial treatment period of up to 6 cycles of chemotherapy treatment (approximately 7 months) for all patients. Follow up will be 6 months after registration or 1 month after the end of treatment if 6 cycles of chemotherapy was administered.

Trial data will be recorded by UK NAC and RHCs research staff on the CRFs and submitted to the LEEDS CTRU. It is the responsibility of each trial site to retain copies of all completed CRFs and to maintain their Investigator Site File which contains all essential documentation for the trial that is required at site.

5ml serum samples will be sent to the UK NAC by the RHCs for central testing as part of routine clinical practice; as noted in the following sections of the protocol. Packs, containing appropriately labelled sample tubes for the central testing associated with this trial, will be provided to participating RHCs by the UK NAC.

The central investigations are of key importance in relation to the in-depth assessment of the disease, prognostic factors, and the analysis of response to treatment and outcome.

See Trial Contacts at the beginning of the protocol for addresses for sending samples for central analysis and CRFs.

Assessment summary table:

Investigation	Baseline (Registration at UK NAC)	Re- confirmation of Eligibility (at RHC) ^e	Treatment			Prior to beginning of 4 th Cycle (at UK NAC)	End of treatment visit (at RHC)	Follow up visit (at UK NAC)
			Carfilzomib and Dexamathasone days 1, 8, 15		Thalidomide days 1-28			
			Prior to each treatment cycle (at RHC) ^f	Day 8				
Informed consent	X							
Patient details (including initials, date of birth, sex)	X							
Medical History	X							
Physical Examination ^a	X	X	X			X	X	X
Laboratory tests ^b	X ^b	X	X	X ⁱ	X ⁱ	X	X	X ^b
Pregnancy test	X	X	X ^h			X	X	X ⁱ
Assessment of response at UK NAC						X		X
Echocardiography incl. Tissue Doppler	X		X ^g			X ^g		X
24 Hour Holter monitor	X							
Bone marrow examination ^c	X							
Adverse Events	X	X	X	X	X	X	X	X
Concomitant Medication	X	X	X	X	X	X	X	X
Hepatitis B test	X							
5ml serum sample to UK NAC ^d Used to assess response to treatment			On Day 1 of treatment cycle 1, 2, 3, 5, 6 (to be taken at RHC and sent to UK NAC) AND within a week of the planned start date of the 4 th cycle					

^a Including height, weight, lying and 5 minute standing blood pressure, ECOG performance status

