11.2 Assessments during treatment

Prior to each chemotherapy cycle

During treatment the patient should be seen prior (within 3 days) to each chemotherapy cycle and the following assessments performed:

- Physical examination, including lying and 5 minute standing blood pressure.
- FBC (Hb, White Cell Count, Platelets), clotting screen (PT, APTT, Factor X (if indicated)), biochemistry (urea, creatinine, eGFR, calcium, phosphate, CRP, ALP, GGT, AST, ALT, bilirubin, albumin, sodium, potassium).
- Assess and record any adverse events
- Record concomitant medications
- Repeat echocardiogram at end of cycle 2 only (echocardiograms at baseline, prior to cycle 4 and end of treatment will be done at UK NAC). Echocardiogram to be repeated at any cycle if clinically indicated for unexpected worsening of cardiac function.
- Pregnancy test
- **A 5ml serum sample must be sent to the UK NAC as per standard practice prior to the start of each chemotherapy cycle ***

*The 5 ml serum sample is used by the UK NAC to assess haematological response and relapse (through biochemical tests including serum free light chain assessments), the results of which will be used as part of the trial dataset. The sample will be frozen and stored at the UK NAC indefinitely as per standard practice (separate written

consent is obtained for this as per standard clinical practice for all patients attending UK NAC). In addition, the following data will be collected for each treatment cycle:

- Treatment cycle number and cycle details, including dose given, dose alterations, and reasons
- Toxicities relating to treatment

Day 8 and day 15 of cycle

Patients will also be seen on day 8 and day 15 of each cycle and the following assessment performed:

- FBC (Hb, White Cell Count, Platelets) and creatinine
- Assess and record any adverse events
- Record concomitant medications

All patients with stage III disease will be assessed once weekly for the first three cycles for signs or symptoms of worsening heart failure or “red flag” symptoms .**

All patients will be given a card for “red flag” symptoms with advice to seek urgent medical attention**

** **Red Flag symptoms:** Significant worsening dyspnoea, hypotension, unexplained persistent dizziness, syncopal episodes.

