The continuation of chemotherapy in this trial beyond the third cycle depends on assessment and classification of response at the end of the third cycle of treatment. An Investigator at the UK NAC will send a confirmatory letter from the UK NAC about the classification of response and further treatment though treatment for the next cycle may commence immediately if indicated.

Patients will be seen at the UK NAC after three cycles and either 6 months after registration or in patients receiving a full 6 cycles of chemotherapy, 1 month after the final cycle of treatment.

Thereafter, patients will be monitored off protocol as per their clinical need.

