18.3 Endpoint definitions

- DLT and MTD are defined in section 8.1.4 and 8.1.5
- The proportion of patients treated who experience any grade 3 or 4 CTCAE toxicity will be calculated as number of patients who experience any grade 3 or 4 CTCAE toxicity throughout their treatment cycle.
- Clonal response rate (based on paraprotein and FLCs) is defined as the proportion of patients who achieve at least a PR within 3 months, at 3 months, within 6 months and at 6 months after trial registration.
- Amyloidotic organ response rate is defined as the proportion of patients who achieve organ response within 3 months and within 6 months of trial registration.
- Time to Amyloidotic organ response is defined as the time from the dose allocation to first achieving organ response.
- The number of patients experiencing dose delays will be defined as the number of patients experiencing delays in treatment with any of the study treatments.
- KTD compliance: Patients will be regarded as compliant to treatment where treatment is received as per protocol until withdrawal from treatment and have no more than 1 dose omission of Carfilzomib, 5 of Thalidomide or 1 of Dexamethasone during each cycle.
- Relative Dose intensity will be calculated as the percentage ratio between the received and planned dose intensities, where dose intensity is the cumulative dose divided by the duration of treatment.

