2.3.2 Secondary endpoints

Clonal response rate (based on paraprotein and FLCs) is defined as the proportion of patients who achieve at least a PR within 3 months, at 3 months, within 6 months and at 6 months after trial registration.

Amyloidotic organ response rate is defined as the proportion of patients who achieve organ response within 3

months and within 6 months of trial registration.

Time to Amyloidotic organ response is defined as the time from the dose allocation to first achieving organ response.

The number of patients experiencing dose delays will be defined as the number of patients experiencing delays in treatment with any of the study treatments.

KTD compliance: Patients will be regarded as compliant to treatment where treatment is received as per protocol until withdrawal from treatment and have no more than 1 dose omission of Carfilzomib, 5 of Thalidomide or 1 of Dexamethasone during each cycle.

Relative Dose intensity will be calculated as the percentage ratio between the received and planned dose intensities, where dose intensity is the cumulative dose divided by the duration of treatment.

3. Analysis Sets

Statistical analysis will be descriptive for all endpoints, and will be summarised overall and by dose cohort. All safety analyses will be based upon the safety analysis set; safety data from patients not included in this analysis set will be listed separately. All efficacy analyses will be based upon the per protocol set. Patients who do meet the criteria to be included in each of analysis sets will have the reasons for emission listed. A sensitivity analysis on the efficacy endpoints may be considered if the total number of patients in each of the analysis sets differs by more than 3 patients.

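### The 3-month response rates run from registration although dosing may start up to 70 days later, and six-cycle completers' final visit falls after the 6-month cut-off

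*Protocol*

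**What the plan says.** **Time origin.** Protocol 18.3 counts as clonal responders those with "at least a PR within 3 months, at 3 months, within 6 months and at 6 months after trial registration". SAP 2.3.2 repeats the timing: "within 3 months, at 3 months, within 6 months and at 6 months after trial registration". The organ response rates within 3 and within 6 months also run from registration. Time to organ response instead starts at dose allocation, and neither document gives an origin for time to maximum response.

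**Start of treatment.** Registration comes before referral to the Regional Haematology Centre (RHC). Protocol 7.1 then allows two waits in sequence. The first is to the RHC visit, "which must be within 28 days of registration". The second is to dosing: "Patients must start treatment within 6 weeks of completion of the initial eligibility confirmation form at the RHC".

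**Response assessment.** Protocol 11.2 says: "A 5ml serum sample must be sent to the UK NAC as per standard practice prior to the start of each chemotherapy cycle". The table in Protocol 11.0 lists day 1 of cycles 1, 2, 3, 5 and 6, plus a sample "within a week of the planned start date of the" fourth cycle. UK NAC assesses response before cycle 4, and continuing treatment "depends on assessment and classification of response at the end of the third cycle of treatment". Nothing ties the 3-month rates to that assessment or gives them a window.

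**Final visit.** Protocol 11.0 states: "The trial consists of an initial treatment period of up to 6 cycles of chemotherapy treatment (approximately 7 months) for all patients". Six-cycle completers are seen at UK NAC one month after the last cycle, and other patients 6 months after registration (Protocol 9.4, 11.2, 11.3).

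**Analysis.** SAP 5.1 keeps patients with missing data in the denominator of the relevant population. For efficacy this is the per protocol set, which requires at least one carfilzomib dose and one post-baseline efficacy assessment (SAP 3.3). Protocol 19.1 makes the clonal response rate the main measure of activity.

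**The concern.** One proportion mixes patients with very different exposure. A patient dosed in the first week after registration is judged after three cycles; one dosed two months after registration is judged after one cycle or none. The gap reflects referral and scheduling, not the regimen. The expansion phase is meant to inform later trials (Protocol 3.1), so a 3-month rate lowered by start delay could be carried forward as a property of KTD.

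The 6-month organ response rate has a related gap. The last UK NAC assessment of patients who complete treatment falls after the cut-off, so a response first documented there cannot count.

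**Working it through.** The plan gives no figure on this point, so there is none to reproduce.

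**Inputs.** RHC visit up to 28 days after registration, and first dose up to 42 days after the initial eligibility form (Protocol 7.1, 11.1.2). Cycles of 28 days, at most six (Protocol 1.1). Pre-cycle visits up to 3 days early (Protocol 11.2); pre-cycle-4 sample up to a week early (Protocol 11.0). Assumed: 3 months = 91 days, 6 months = 183 days, no cycle delays, and the form completed at the RHC visit. L is the number of days from registration to first dose.

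**1. Range of L.** 0 to 28 + 42 = 70 days.

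**2. Post-treatment serum samples by day 91.** The cycle 1 sample is pre-treatment. On-day samples fall at L+28, L+56 and L+84, so they count if L is at most 63, 35 and 7. At the earliest they fall at L+25, L+53 and L+77, so L must be at most 66, 38 and 14.

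| L, on-day sampling | L, earliest sampling | Samples by day 91 |
|---|---|---|
| 0–7 | 0–14 | 3 |
| 8–35 | 15–38 | 2 |
| 36–63 | 39–66 | 1 |
| 64–70 | 67–70 | 0 |

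Taking 90 or 92 days moves each cut by one day. One permitted 14-day delay before cycle 2 (Protocol 10.2) puts the first on-day sample at L+42, so none falls by day 91 once L is 50 or more.

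**3. Carfilzomib doses due by day 91.** Doses fall on L + 28(c − 1) + {0, 7, 14} for cycle c. The count is 11 at L = 0, 8 at L = 28, 6 at L = 42 and 3 at L = 70.

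**4. Illustration only.** If L were spread evenly over 0–28, 0–42 or 0–70 days, the pre-cycle-4 assessment would count for 8/29 = 28%, 8/43 = 19% or 8/71 = 11% of patients on-day. At the earliest sampling the shares are 15/29 = 52%, 15/43 = 35% or 15/71 = 21%. Assume also cumulative response of 30/50/60% after one, two and three cycles (range 20/40/60 to 40/55/60). A true 60% after three cycles would then be recorded on-day as:
- 0–28 days: (8×60 + 21×50)/29 = 53% (46–56)
- 0–42 days: (8×60 + 28×50 + 7×30)/43 = 49% (40–53)
- 0–70 days: (8×60 + 28×50 + 28×30 + 7×0)/71 = 38% (30–44)

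With the earliest sampling the figures are 55% (50–58), 52% (45–55) and 41% (34–47). Neither the delays nor the response curve comes from the documents.

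**5. Completers' final visit.** Six cycles take 6 × 28 = 168 days. One month later is day 196 to 199 from first dose, 13 to 16 days after day 183. From registration it is day 196 to 199 + 70 = 269.

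**6. Clonal response within 6 months.** Cycle 6 day 1 is at L+140, by day 183 if L is at most 43, which gives five post-treatment samples. Otherwise there are four, since cycle 5 day 1 is at L+112 = 182 even at L = 70.

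**7. Effect of moving the origin.** Counted from first dose, an on-schedule patient has samples on days 28, 56 and 84, all by day 91 whatever L is. The completers' visit still falls after day 183, so the new origin repairs the 3-month rates but not the 6-month organ rate.

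**The case against.** **The endpoint is what it says.** Both documents consistently define response by time from registration, and neither calls it response after three cycles. The analysis is descriptive, and the continuation decision already uses the end-of-cycle-3 assessment. This stands as a limit on the consequence. It does not make the rate a good description of KTD activity.

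**Other summaries recover part of the loss.** Maximum clonal response is reported within six cycles of treatment, and time to organ response by Kaplan–Meier has no 6-month limit (Protocol 19.4; SAP 5.3.2, secondary endpoints). A reader might infer that organ responses first seen at the final visit disappear from the report. They do not: they are missing only from the 6-month proportion. Some heart and liver responses can also be dated earlier, from NT-proBNP and alkaline phosphatase before each cycle and from interim echocardiograms (Protocol 11.0, Appendix 6).

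**The denominator rule is narrower than it looks.** SAP 5.1 might be read as keeping every unsampled patient in the denominator. It applies within the per protocol set. A late starter first sampled after day 91 stays; a patient never assessed after baseline is excluded.

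**Long delays are the edge of the window.** Zero samples needs a first dose on about day 64 to 70 without cycle delays, and a wait of 21 days or more requires a second eligibility form. This stands for the extreme case. Losing the pre-cycle-4 assessment takes a delay of only 8 days (15 with the earliest sampling).

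**Conclusion.** The point holds for the 3-month clonal and organ response rates and for the 6-month organ response proportion. Start delay can only reduce the treatment received and the samples available by day 91, so the 3-month rates tend to sit below the response after three cycles.

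The size is unknown. The documents give no actual delays, and a reader might take the illustrated 38–55% against 60% as an estimate of bias; it is not one. If the recommended-dose cohort has 20 + 6 = 26 patients, one responder is 1/26 = 3.8 points.

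Nor do the documents support the broader inference that the whole activity assessment is compromised. Clonal response within 6 months is little affected, maximum response within six cycles is not limited in this way, and all these endpoints are secondary.

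The conclusion rests on the assumptions listed with the inputs. If the eligibility form is completed after the RHC visit, L could exceed 70 days. If the final month ran from the last carfilzomib dose instead of the end of cycle 6, the completers' visit would be borderline at L = 0 (154 + 28 to 154 + 30 = day 182 to 184).

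**What to change.** (a) In Protocol 18.3 and SAP 2.3.2, time the 3-month clonal and organ response rates from first carfilzomib dose. Response within 3 months is then by day 91 from first dose. Response at 3 months is the pre-cycle-4 assessment (day 77 to 84 on schedule) within a fixed, stated window around 3 months from first dose. The window must be fixed: three 14-day delays would move that assessment to 84 + 42 = day 126 and give delayed patients longer to respond. Count per protocol patients with no assessment in the window as non-responders. Do not count responses first seen after non-trial therapy starts, since early stoppers may be treated off trial (Protocol 9.4).

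(b) Measure time to organ response and time to maximum response from first dose.

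(c) Keep deaths and progression-free status at 6 months from registration, and say so. Early stoppers' last visit and the minimum follow-up (Protocol 19.5) are set from registration.

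(d) Keep the within-6-months rates. Add organ response by the final UK NAC visit, reported separately for six-cycle completers and early stoppers, with the same exclusion for non-trial therapy.

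(e) Reconcile the final-visit times for patients who do not complete six cycles. Protocol 9.4, 11.2 and 11.3 and Appendix 6 footnotes \*, \*\* and \*\*\*\* set 6 months after registration. The Appendix 6 lists of clinical, haematology and biochemistry assessments set 7.5 months after start of treatment. Its echocardiography footnote (\*\*\*) sets 6 months after start of treatment. Only under the first reading is the early stoppers' visit on day 183 − 70 = 113 to 183 from first dose.

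**Cost.** Parts (a) to (d) are wording and use existing visits and samples. The start date of non-trial therapy must be available; concomitant medication is already listed for the follow-up visit. No patient is lost, because the per protocol set already requires a carfilzomib dose. Part (e) may move the early stoppers' visit. The 3-month rates leave the registration clock, and patients with long cycle delays may fall outside the window.

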19.0 Statistical considerations

19.1 Sample size

In the dose escalation phase of this study, a minimum of 6 (3 at dose level 0 and 3 at dose level -1) and a maximum of 18 (6 at dose level 0 1 and 2) patients will be recruited in a 3+3 design with cohorts of between 3 and 6 patients, in order to determine maximum tolerated dose and recommended dose.

At the recommended dose level identified, a further 20 patients will be recruited to further assess safety and toxicities at the RD.

The secondary objective of assessing activity will be primarily assessed by the clonal response rate.

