1.0 Protocol Summary

1.1 Summary of Trial Design

Title:	A single arm open labeled multicentre phase 1b dose escalation study of Carfilzomib taken in combination with Thalidomide and Dexamethasone in relapsed AL amyloidosis (CATALYST Trial)
EudraCT no:	2015-000954-40
Sponsor name & no:	University College London 14/0786
Funder name & no.:	Amgen 20159879
ISRCTN no:	16308011
Design:	Open label, multi-centre, Phase Ib clinical trial
Aims:	To determine the maximum tolerated dose of Carfilzomib within a combination chemotherapy regimen (KTD) and to assess the safety and tolerability of this regimen in patients with relapsed or refractory AL amyloidosis
Primary endpoint:	Define the MTD and RD of Carfilzomib in combination with TD Safety and toxicity of KTD
Secondary endpoints:	Clonal responses Improvement in amyloidotic organ function Overall Survival at 1 year Relapse free survival at 1 year
Subjects:	Any UK patient with a diagnosis of systemic AL amyloidosis with relapsed or refractory disease after first line treatment. During the dose escalation phase a minimum of 6 or a maximum of 18 participants will be recruited. Once the MTD and/or RD has been established a maximum of 20 participants will be recruited.

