Statistical summary:	
Sample Size
 
In the dose escalation phase of this study, a minimum of 6 (3 at dose level 0 and 3 at dose level -1) and a maximum of 18 (6 at dose level 0, 1, and 2) patients will be recruited in a 3+3 design with cohorts of between 3 and 6 patients, in order to determine maximum tolerated dose (MTD) and recommended dose (RD). At the recommended dose level identified, a further 20 patients will be recruited to further assess safety and toxicities at the RD.
 
Analysis sets and dose cohorts
 
All patients that receive at least one dose of Carfilzomib will be included in the safety analysis set.
 
The per protocol analysis set will include all patients with at least one post baseline efficacy assessment who receive at least one dose of Carfilzomib and have no protocol deviations with relevant impact on efficacy.
 
Determination of the MTD in the dose escalation phase of the trial will be based on those patients who have received at least one cycle KTD and will be evaluated between the time of receiving the first dose of Carfilzomib in cycle 1 and the first dose of treatment in cycle 2. The safety review committee will review each DLT and attribute the DLT to the loading dose or the registered dose; any DLT attributed to the loading dose will be excluded when determining the MTD. KTD Patients who do not receive one complete cycle due to experiencing a DLT will be included in the analysis; patients who do not receive at least one complete cycle for reasons other than toxicity, without experiencing a DLT, and who miss a dose of Carfilzomib, more than 14 doses of Thalidomide or 2 doses of Dexamethasone in the first cycle, will be replaced. Evaluability will be considered by the safety review committee on an individual basis to account for attributing DLTs and missed doses to the loading or the registered dose. The RD cohort will include all patients who are registered to receive and receive at least one dose of Carfilzomib at the RD. This cohort will include patients from the dose escalation and dose expansion phases of the study. All patients who do not fulfill this criteria will be included in the non-RD cohort.
 
All safety analyses will be based upon the safety analysis set; safety data from patients not included in this analysis set will be listed separately. All Efficacy analyses will be based upon the per protocol set.
 
Primary endpoints and analysis
 
The number of patients experiencing DLTs within the first cycle of KTD will be presented, with descriptive summaries of the specific DLTs observed. Summaries will be presented for each dose level. This data will be presented for patients registered to the dose escalation phase of the study only.

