8.1.3 Dose Escalation

Dose escalation will begin at DL0 and will proceed until MTD or the highest planned dose level has been reached. Toxicity data for each cohort will be reviewed by the Safety Review Committee prior to dose escalation, according to the following schema (Table 2).

Table 2. Scheme for dose escalation decision

Identifying MTD	
Number of patients with a DLT following 1 cycle at a given dose level	Escalation decision rule
0 out of 3	Enter 3 patients at the next highest dose level. If current dose level is the highest dose level, this is the MTD; proceed to identifying RD
≥2 out of 3	Dose escalation stopped and next lowest dose identified as MTD. Proceed to identifying RD. If current dose level is lowest dose, no MTD identified.
1 out of 3	Enter 3 more patients at the current dose level. 
 • If 0 out of these additional 3 experience DLT (i.e. total DLTs 1/6), proceed to the next highest dose level. If current dose level is the highest dose level, this is the MTD & current dose level is identified as RD • If 1 or more of these additional 3 experience DLT (i.e. total DLTs >1/6), dose escalation stopped

	and next lowest dose identified as MTD. Proceed to identifying RD

Identifying RD
 
Once the MTD is identified, at least 6 patients must have completed cycle 1 at the RD before enrolment to the dose expansion phase can commence.
 
The RD is defined as the highest dose level at which at most 1/6 patients experience a DLT. If only 3 patients have been treated at the next lowest dose an additional 3 patients are recruited to this dose level. If >1/6 DLTs are then experienced at this dose level, dose level de-escalation continues until the RD is identified.
 
If the MTD is identified as the highest dose level with 0/3 DLTS then an additional 3 patients are recruited to this highest dose level. If >1/6 DLTs are then experienced at this dose level, dose level de-escalation continues until the RD is identified. If ≤1/6 DLTs are experienced then the highest dose level is identified as the RD.
 
If no MTD is identified, no RD is identified and the study will not continue to the dose expansion phase.
	

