19.2 General Considerations

Statistical analysis of clinical endpoint data is the responsibility of the CTRU Statistician. A full statistical analysis plan will be written before any analyses are undertaken. The analysis plan will be written in accordance with current CTRU standard operating procedures and will be finalised and agreed by the following people: the trial statistician and supervising statistician, the Chief Investigator, the CTRU Delivery and Scientific Leads and the Senior Trial Manager. Any changes to the finalised analysis plan, and reasons for changes, will be documented.

All patients that receive at least one dose of Carfilzomib and with no protocol deviations with relevant impact on safety will be included in the safety analysis set.

The per protocol set will include all patients with at least one post baseline efficacy assessment who receive at least one dose of Carfilzomib and have no protocol deviations with relevant impact on efficacy.

Determination of the MTD in the dose escalation phase of the trial will be based on those patients who have received at least one cycle KTD and will be evaluated between the time of receiving the first dose of Carfilzomib in cycle 1 and the first dose of treatment in cycle 2. The safety review committee will review each DLT and attribute the DLT to the loading dose or the registered dose; any DLT attributed to the loading dose will be excluded when determining the MTD.

KTD Patients who do not receive one complete cycle due to experiencing a DLT will be included in the analysis; patients who do not receive at least one complete cycle for reasons other than toxicity, without experiencing a DLT, and who miss a dose of Carfilzomib, more than 14 doses Thalidomide or 2 doses of Dexamethasone in the first cycle, will be replaced. Evaluability will be considered by the safety review committee on an individual basis to account for attributing DLTs and missed doses to the loading or the registered dose.

The RD cohort will include all patients who are registered to receive and receive at least one dose of Carfilzomib at the RD. This cohort will include patients from the dose escalation and dose expansion phases of the study. All patients who do not fulfil these criteria will be included in the non-RD cohort.

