1.4 Sample size and expected accrual

In the dose escalation phase of this study, a minimum of 6 (3 at dose level 0 and 3 at dose level -1) and a maximum of 18 (6 at dose level 0 1 and 2) patients will recruited in a 3+3 design with cohorts of between 3 and 6 patients, in order to determine maximum tolerated dose and recommended dose.

At the recommended dose level identified, a further 20 patients will be recruited to further assess safety and toxicities at the RD.

The study will run in 15 UK centres. The study duration is expected to be approximately 42 months – including 6 months of set up, 24 months of recruitment, 6 months of follow-up and 6 months of analysis/write-up.

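### The stated escalation-phase maximum of 18 patients omits dose level -1 and replacements; the natural reading of Table 2 allows up to 24 evaluable patients

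*Protocol*

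**What the plan says.** Four places give the size of the escalation phase.

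- Protocol 19.1 Sample size, for determining both the MTD and the RD. The lower limit is "a minimum of 6 (3 at dose level 0 and 3 at dose level -1". The upper limit, in the same sentence, reads "and a maximum of 18 (6 at dose level 0 1 and 2) patients".
- Protocol 1.1, Subjects row: "During the dose escalation phase a minimum of 6 or a maximum of 18 participants will be recruited".
- Protocol 1.1, Statistical summary: "a maximum of 18 (6 at dose level 0, 1, and 2) patients will be recruited in a 3+3 design".
- SAP 1.4: "a maximum of 18 (6 at dose level 0 1 and 2) patients".

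The dose rules are in Protocol 8.1.3, Table 2. Escalation starts at level 0. Once the MTD is identified, "at least 6 patients must have completed cycle 1 at the RD before enrolment to the dose expansion phase" can begin. A lower level that has had only three patients receives three more, and so does the highest level after 0/3 DLTs. Then: "If >1/6 DLTs are then experienced at this dose level, dose level de-escalation continues until the RD is identified". Level -1 (27 mg/m²) is a listed dose in Table 1.

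Protocol 19.2 and SAP 3.4 provide for replacement of "patients who do not receive at least one complete cycle for reasons other than toxicity, without experiencing a DLT", if they also miss specified doses in cycle 1. Neither gives a number or a limit.

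**The concern.** The same sentence uses level -1 to build its minimum and leaves it out of its maximum. Because the sentence covers finding the RD as well as the MTD, the extra patients treated while de-escalating to the RD belong in the count. Table 2 does not stop that de-escalation at level 0.

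Also, 18 is six evaluable slots at each of three levels, yet it is presented as the number recruited. A trial that needs all 18 slots and replaces one patient passes the stated figure without using level -1.

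At stake is a stated enrolment ceiling. If toxicity at several levels forced the trial down to level -1, following Table 2 could require more patients than the sample-size text permits, and the documents do not say which text gives way.

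**Working it through.** **Inputs.** The levels (-1, 0, 1, 2), the start at level 0, the 3+3 rule and the RD step come from Protocol 8.1.1 and Table 2. The documents give no DLT rates, so every rate below is an assumption.

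**1. The plan's own figures.** Maximum: 3 levels × 6 = 18. Minimum: at least 2/3 DLTs at level 0, then at least 2/3 at level -1, gives 3 + 3 = 6. Both reproduce.

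**2. All paths through Table 2.** Exact enumeration gives evaluable totals of 6, 9, 12, 15, 18, 21 and 24. The largest total on any path that never uses level -1 is 18, which is probably how the figure arose. Totals above 18 occur in three configurations:

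| Level -1 | Level 0 | Level 1 | Level 2 | Total |
|---|---|---|---|---|
| 3 | 6 | 6 | 6 | 21 |
| 6 | 6 | 6 | 3 | 21 |
| 6 | 6 | 6 | 6 | 24 |

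A path to 24: 0/3 at levels 0, 1 and 2; three more at levels 2, 1 and 0 in turn, each bringing that level above 1/6; then six at level -1.

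**3. Probability of more than 18 evaluable patients.** Such a path needs 0/3 at both level 0 and level 1, then at least two DLTs among the next three patients at each. (A level passed with 1/6 would itself be the RD on the way down.) For DLT rate p, write T(p) = 3p² − 2p³ for the probability of at least 2 DLTs in 3 patients, and define:

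- A(p) = (1 − p)³ × T(p), used at levels 0 and 1;
- F3 = T(p₂), level 2 stopped after three patients;
- F6 = (1 − p₂)³ × T(p₂) + 3p₂(1 − p₂)² × [1 − (1 − p₂)³], level 2 failed after six;
- G = 1 − T(p₋₁), level -1 taken to six.

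Then P(N > 18) = A(p₀) × A(p₁) × (F6 + F3 × G), and P(N = 24) = A(p₀) × A(p₁) × F6 × G.

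At 20/30/40/50% (levels -1/0/1/2):

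- A(0.30) = 0.343 × 0.216 = 0.07409 and A(0.40) = 0.216 × 0.352 = 0.07603; their product is 0.005633.
- F3 = 0.5; F6 = 0.125 × 0.5 + 0.375 × 0.875 = 0.3906; G = 0.896.
- P(N > 18) = 0.005633 × (0.3906 + 0.448) = 0.0047.
- P(N = 24) = 0.005633 × 0.3906 × 0.896 = 0.0020.

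Results from the enumeration, which agree with the formula:

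| Assumed DLT rates, % (-1/0/1/2) | P(N > 18) | Expected N |
|---|---|---|
| 5/5/5/5 | 0.000001 | 12.7 |
| 5/10/15/20 | 0.00026 | 13.1 |
| 30/30/30/30 | 0.0029 | 11.6 |
| 10/20/30/45 | 0.0033 | 12.3 |
| 20/30/40/50 | 0.0047 | 11.4 |

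The last row is the highest of 12 curves tried. Over all 330 non-decreasing curves with rates from {5, 10, 20, 30, 40, 50, 60, 70}%, the highest P(N > 18) is 0.0057 (at 5/40/40/70) and the highest P(N = 24) is 0.0024 (at 5/40/40/40).

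This does not hinge on the grid. A(p) peaks at p ≈ 0.36 with value 0.0775, and the bracket cannot exceed 1. No curve can therefore give more than about 0.0775² = 0.006.

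**4. Replacements.** Recruited = evaluable + replaced. In a trial that needs exactly 18 evaluable patients (1.6% to 8.1% of trials on the 12 curves), one replacement takes recruitment to 19. How often that would happen depends on a non-evaluability rate that the documents do not give, so no probability is attached.

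**The case against.** **The 18 is itself a cap.** The Subjects row of Protocol 1.1 limits recruitment to 18, so a reader might infer too much from saying that nothing restrains Table 2. That stands: read literally, the two texts conflict, and which one yields is the sponsor's decision. The conflict is the point.

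**The 24 is inferred.** Table 2 spells out adding three patients at a next-lower level that has three, and at the highest level. It has no explicit step for opening an untreated level -1 late in the RD stage. The total of 24 follows from continued de-escalation together with the six-at-RD requirement. That is the natural reading, but not a stated number.

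**The 18 counts evaluable slots, and replacement is already disclosed.** This is fair; the replacement rule appears in the same statistical summary as the 18. What remains is that the text says recruited and does not say that replacements are extra. The rule is also narrow, so a reader should not infer that replacements are likely to push the trial past 18. The documents support no rate.

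**It hardly matters.** Largely true. Several paths that use level -1 still end at or below 18. All analyses are descriptive (Protocol 19.2, SAP 5.2), so no power or estimate rests on the figure. Recruitment halts after each group of three (Protocol 19.5), and the Safety Review Committee decides each step (Protocol 16.3.2). But those decisions follow the Section 8 rules, so applying the rules correctly is what would pass the stated maximum.

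**Conclusion.** The stated maximum is wrong as a bound, and the correction is minor. On the natural reading of Table 2 the maximum is 24 evaluable patients against 18 stated, a difference of 6 (6/18 = 33%). Replacements come on top of either figure.

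Exceeding 18 evaluable patients is rare: below 0.6% on every assumed DLT curve tried. That result rests on binomial DLTs and the reading of Table 2 set out above. Expected evaluable enrolment is about 11 to 13 on the assumed curves.

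A reader might infer that the dose-finding rules are faulty or that the selected dose could change. The documents do not support that: Table 2 and the MTD definition work without reference to the 18.

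**What to change.** In the escalation clause only, in Protocol 1.1 (Subjects and Statistical summary), Protocol 19.1 and SAP 1.4, state: *a minimum of 6 and a maximum of 24 evaluable patients (6 at each of dose levels -1, 0, 1 and 2), plus replacements for patients not evaluable for the MTD.*

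Leave Table 2 and the MTD definition alone. Leave the expansion wording alone too: the Subjects row sets 20 as a ceiling there, and carrying over the 19.1 phrasing of a further 20 would turn it into a fixed number. If the sponsor prefers to keep 18, the lesser alternative is to say that it excludes level -1 and replacements.

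The cost is a text amendment in two documents, with ethical and regulatory approvals as appropriate (Protocol 21.4), and a stated maximum that looks less favourable. The design, the dose rules and expected enrolment do not change. It can wait for the next amendment.
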